6.3.2 Prohibited Concomitant Medications

Oral corticosteroid medications may not be used prophylactically with the first dose. Chronic administration of oral corticosteroids at a stable dosage for at least 30 days prior to enrollment are permitted. The reason(s) for ancillary therapy, including dosage and date(s) of treatment, will be recorded in the source documents. Use of ivacaftor (Kalydeco™) or lumacaftor are prohibited within 45 days of Day 1, through the End of Study visit. Use of any investigational drug (other than QR-010) or device are prohibited within 30 days of Day 1, through the End of Study visit. If the subject received therapy with ivacaftor or lumacaftor within 90 days prior to Day 1, the start and stop dates will be recorded in the source documents and CRF.

6.3.3 Adequate Forms of Birth Control

Women of child bearing potential must agree to use a highly effective method of birth control from the list below (defined as those, alone or in combination, that result in a low failure rate, ie, less than 1% per year when used consistently and correctly). Double barrier methods (a combination of condom with cap, diaphragm, or sponge with spermicide) are not considered

highly effective. Childbearing potential is defined as being fertile following menarche and until becoming post-menopausal, unless permanently sterile. Permanent sterilization methods include hysterectomy, bilateral salpingectomy and bilateral oophorectomy.

Highly effective methods of birth control include:

- Combined (estrogen and progesterone containing) hormonal contraception associated with inhibition of ovulation (oral, intravaginal, transdermal)
- Progesterone-only hormonal contraception associated with inhibition of ovulation (oral, injectable, implantable)
- Intrauterine device (IUD)
- Intrauterine hormone-releasing system (IUS)
- Bilateral tubal occlusion
- Vasectomized partner (provided that partner is the sole sexual partner and has received medical assessment of the surgical success)
- Sexual abstinence. Sexual abstinence must be true abstinence which is the preferred and usual lifestyle of the subject. Periodic abstinence (eg, calendar, ovulation, symptothermal, post-ovulation methods), declaration of abstinence for the duration of the trial, and withdrawal are not acceptable methods of contraception.

Birth control measures must be employed during the time of participation (beginning at the Screening Visit) in this trial. Protections against pregnancy must be continued for at least 3 months after the last dose of study drug.

A man is considered fertile after puberty unless permanently sterile by bilateral orchidectomy. Male subjects with CF with medical confirmation of azospermia and/or infertility will be considered permanently sterile. A man who is fertile should use a condom during treatment and until 90 days after the last dose of study drug.

6.4 Adverse Reaction Management

AEs in the study will be treated with appropriate therapies. Acute bronchospasm (defined as a $\geq 15\%$ decrease in FEV₁ % predicted) should be treated with treatment cessation and with β_2 agonists, IV hydrocortisone (100 mg), or other agents as appropriate. Additional supportive care should be provided as necessary by qualified staff with emergency resuscitation equipment.

A Grade 4 (as defined by Common Terminology Criteria for Adverse Events [NCI CTCAE Version 4.03] Modified for CF) adverse reaction requires permanent discontinuation of study drug.

If Grade 2-3 toxicity is noted during the dose administration, the administration should be halted and the subject assessed. If the adverse reaction symptoms resolve promptly, then study drug

administration may be re-initiated. Any Grade ≥ 2 adverse reaction suspected of being related to study drug will result in study drug discontinuation.

7.0 EVALUATIONS BY VISIT

All tests and procedures are detailed in Appendix 1, Schedule of Assessments. All laboratory tests are detailed in Appendix 2, Schedule of Laboratory Assessments. Refer to these appendices for the required assessments for each study day. Throughout the protocol, the term “baseline” is used to refer to tests or procedures performed at screening, Day -1, or on Day 1 prior to dosing.

7.1 Visit and Assessment Windows

The flexibility regarding scheduling of study days and corresponding procedures differ depending on the cohort and phase of the study. The timing of assessments, procedures and sample collections outlined in the protocol are nominal times. It is understood that in the phase 1 setting, actual times will approximate rather than match the nominal times exactly. Actual times are to be recorded in the source documentation and in the case report forms (CRFs), and, if any time points are missed, the reasons are also recorded.

For the SAD cohorts, there is no flexibility regarding the timing of the scheduled study days in relation to dose Day 1.

For the MAD cohorts, there is some flexibility regarding the timing of the scheduled study days in relation to dose Day 1. The description of procedures assumes a Monday-Wednesday-Friday dosing schedule. An alternative dosing schedule can be used, provided that there is at a minimum 2 days between doses, and a maximum of 4 days between doses. Missed doses are to be recorded as such, and the overall treatment period should remain at 4 weeks, and not be extended to accommodate the missed doses. Missed doses are to be recorded in the CRF.

Details regarding acceptable windows for timing of study procedures for both the SAD and MAD cohorts can be found in the Laboratory Manual.

7.2 Screening Visit (All Cohorts)

A screening log of all consented subjects will be kept at each site. Subject screening should be conducted ≤ 14 days prior to study drug dosing (Day 1). Screening evaluations may be completed over several days, if necessary.

If the first administration of study drug does not occur within the initial 14 days of screening, the screening period may be extended up to an additional 14 days and subjects may be reassessed for eligibility with an interim medical history, focused physical examination, and repeat of laboratory studies (standard laboratory assessments).

At the discretion of the Sponsor’s Medical Monitor, the screening period for an individual subject may be extended for an additional 7 days. In this case, the subject may be reassessed for

eligibility with an interim medical history and repetition of all screening assessments, with the exception of sweat chloride, 12-lead ECG, chest Xray and CFTR genotyping.

If the screening period extends beyond 28 days (or up to 35 days with concurrence of the Sponsor's Medical Monitor), the potential subject will be considered a screening failure, but may be re-screened at a later date.

All screening evaluations must be reviewed by the Investigator to establish subject eligibility before dosing the subject for this study. Local laboratory results will determine subject eligibility for laboratory criteria.

The following screening evaluations should be obtained for all subjects:

1. Informed consent
2. Review of inclusion/exclusion criteria (Selection of Subjects)
3. Review of medical history
4. Demographics
5. Complete physical examination (including height and body weight)
6. Vital signs: blood pressure, heart rate, respiratory rate, and temperature
7. Oximetry
8. Chest Xray
9. Review of concomitant medication (record all medication within 30 days prior to screening), including prescription medications, over the counter (OTC) medications, herbal preparations, and use of lumacaftor or ivacaftor within 90 days prior to Day 1
10. Twelve-lead ECG
11. Spirometry (FEV₁, FVC, and FEF₂₅₋₇₅)
12. Obtain urine sample for local laboratory assessments
13. Obtain urine or blood sample for drug screen
14. Obtain urine or blood sample for pregnancy test (for women of child-bearing potential)
15. Obtain blood samples for local laboratory assessments
16. Obtain blood and sputum for inflammatory biomarkers
17. Obtain blood sample for CFTR genotyping (if adequate prior documentation is not available)
18. Obtain sample for sweat chloride determination

7.3 SAD Cohorts (Cohorts 1-4)

7.3.1 Day -1 (Start of In-Clinic Phase)

1. Confirm study eligibility
2. Complete physical examination (including body weight)
3. Vital signs: blood pressure, heart rate, respiratory rate, and temperature measured
4. Oximetry
5. Concomitant medication review
6. AE review
7. Obtain blood and urine samples for local laboratory assessments (only assessments that were abnormal but not clinically significant at screening)
8. Obtain urine or blood sample for pregnancy test (for women of child-bearing potential)
9. Obtain sputum sample for the following local laboratory assessment:
 - Microbiology organism identification
10. Obtain blood sample for CFTR sequencing (required, separate consent form may be required). Note: this blood sample may be collected on Day 1 pre-dose instead of Day -1.
11. Obtain blood and sputum samples for inflammatory biomarkers. Note: these blood and sputum samples may be collected on Day 1 pre-dose instead of Day -1.
12. Spirometry (FEV₁, FVC, and FEF₂₅₋₇₅) post administration of short-acting bronchodilator

7.3.2 Day 1

Pre-dose:

1. Symptom-directed physical examination (including body weight)
2. Vital signs
3. Oximetry
4. Concomitant medications review
5. AE review
6. Administer any routine pulmonary medications and airway clearance techniques, including SABA and/or LABA, Pulmozyme, inhaled corticosteroids and/or antibiotics
7. Initiate continuous cardiac and vital signs monitoring and continue for 24 hours post dose
8. Spirometry (FEV₁, FVC, and FEF₂₅₋₇₅)
9. Obtain blood samples for local laboratory assessments
10. Obtain urine sample for urinalysis (Time 0, pre-dose)

11. Obtain blood and urine samples for PK (Time 0, pre-dose)

Study Drug Administration:

Study drug to be administered by qualified site personnel via the designated study nebulizer, until all study drug solution has been administered. Subjects are to be seated during the entire duration of study drug administration, inhaling the nebulized study drug using normal tidal breathing (no noseclips). Details regarding study drug preparation, device preparation and handling, as well as administration of study drug will be included in the Pharmacy Manual and Study Manual.

Post-dose:

1. Symptom-directed physical examination at 15, 60 minutes, 2, 3, 4, 6, 8, and 12 hours post dose
2. Vital signs at 1, 10, 30, 60 minutes, 2, 4, 12 hours post dose
3. Oximetry at 1, 10, 30, 60 minutes, 2, 4, 12 hours post dose
4. Concomitant medications review
5. AE review
6. Spirometry at 10, 30, and 60 minutes, and 2, 4, and 8 hours post dose
7. Obtain blood samples for local laboratory assessments at 30, 60 minutes, 2, 4, 8, and 12 hours post dose
 - Complete blood count (CBC) with absolute differential
 - Serum chemistry
8. Obtain the following samples for PK:
 - Blood at 0.5, 1, 2, 3, 4, 12 hours post dose
 - Pooled urine from 0 to 4 hours, 4 to 12 hours, and 12 to 24 hours post dose. Subjects should empty their bladders just prior to dosing and at the end of each time interval for the final urine collection of that interval. Urinalysis by dipstick will be performed on the pooled urine samples for each time interval.
 - Sputum at 3 times post dose, within the first 6 hours post dose. Suggest obtaining samples in conjunction with performing spirometry at 10, 60 minutes, and 4 hours post dose.

7.3.3 Day 2

1. Symptom-directed physical examination
2. Vital signs
3. Oximetry

4. Review of concomitant medications
5. AE review
6. Spirometry
7. Obtain blood and urine samples for local laboratory assessments 24 hours post dose
8. Obtain the following samples for PK:
 - Blood at 24 hours post dose
 - Urine at 24 hours post dose
 - Sputum at 24 hours post dose
9. Obtain blood and sputum samples for inflammatory biomarkers (24 hours post dose)

7.3.4 Day 3

1. Vital signs
2. Oximetry
3. Concomitant medications review
4. AE review
5. Obtain blood and urine samples for local laboratory assessments 48 hours post dose
6. Obtain the following samples for PK:
 - Blood at 48 hours post dose
 - Urine at 48 hours post dose

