7.4.2 Day -1

1. Confirm study eligibility
2. Complete physical examination (including body weight)
3. Vital signs: blood pressure, heart rate, respiratory rate, and temperature measured
4. Oximetry

5. Concomitant medication review
6. AE review
7. Obtain blood and urine for local laboratory assessments (only assessments that were abnormal but not clinically significant at screening)
8. Obtain urine or blood for pregnancy test (for women of child-bearing potential)
9. Obtain sputum sample for the following local laboratory assessment:
 - Microbiology organism identification
10. Obtain blood samples for CFTR sequencing (required, separate consent form may be required). Note: this blood sample may be collected on Day 1 pre-dose instead of Day -1, and should not be collected if subject already participated in a SAD cohort.
11. Obtain blood and sputum samples for inflammatory biomarkers. Note: these blood and sputum samples may be collected on Day 1 pre-dose instead of Day -1.
12. Spirometry (FEV₁, FVC, and FEF₂₅₋₇₅) post administration of short-acting bronchodilator

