8.5 Laboratory Evaluations

Laboratory evaluations will be performed according to the study schedule. For screening purposes, should the screening period require longer than 14 days (eg, CFTR genotype testing required longer than 14 days), safety evaluations (serum chemistries, hematologies, urinalysis, physical exam, vital signs, spirometry) must be re-obtained for confirmation of eligibility and enrollment into the study.

Serum chemistries will include sodium, potassium, chloride, bicarbonate, blood urea nitrogen (BUN), creatinine, glucose, calcium, phosphorus, SGPT/ALT, SGOT/AST, GGT, alkaline phosphatase, bilirubin (total and direct), uric acid, lactic dehydrogenase (LDH), albumin,

total protein, triglycerides, and cholesterol. Creatinine clearance is to be calculated using the Cockcroft-Gault equation adjusted for actual body weight. At screening, tocopherol (Vitamin E) levels will also be measured.

Hematologies will include a complete blood count: Complete blood count (CBC) with absolute differential (hematocrit, hemoglobin, white blood count, segmented neutrophils, bands, lymphocytes, monocytes, eosinophils, basophils, platelet count).

A Direct Antiglobulin Test (DAT) will also be performed at screening and 7 days after last dose.

Erythrocyte sedimentation rate (ESR) and C-reactive protein (CRP) will be measured at baseline, 24 hours post dose, and End of Study Visit for SAD cohorts, and at baseline, prior to doses 4, 7 and 10, and at the End of Treatment Visit for MAD cohorts. Two baseline measurements will be made; one on Day -1, and the other prior to dosing on Day 1.

Urinalysis (by visual inspection and dipstick) will include color and appearance, specific gravity, pH, protein, glucose, occult blood, ketones, bilirubin, leukocyte esterase, nitrite, and urobilinogen. In addition, microscopic analyses will be performed on samples with abnormal dipstick results. Urine microalbumin will be measured at baseline for SAD and MAD cohorts; end of study for SAD cohorts; and prior to dose 10 and end of study for MAD cohorts. Time of void will be recorded for each urine sample collected. At screening, testing for drugs of abuse will also be performed, specifically for amphetamines, methamphetamines, methylenedioxyamphetamine, cocaine, cannabinoids, phencyclidine, opiates, methadone, barbiturates, benzodiazepines, ethyl alcohol. Urine or blood testing for drugs of abuse is permitted.

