^f Only subjects who experience pulmonary AEs during the study.

^g See Appendix 2 for a detailed schedule of these assessments, broken down by type of specimen and time relative to dose.

^h Only laboratory assessments that are abnormal (but not clinically significant) at screening should be repeated at Day-1.

ⁱ Pregnancy test (preferably serum but urine is accepted) required for women of childbearing potential only.

^j Subjects who are taking concurrent CF therapy should receive this therapy prior to study drug dosing in the order specified in Section 6.3.1.

Table A.1-2: Multiple Ascending Dose Cohorts 5-8, WEEK 1

Dosing Schedule assumes Monday-Wednesday-Friday dosing:

| Study Procedures | Screening | | Dose 1 | Dose 2 | | Dose 3 | | |
|----------------------------------------|------------------------|----------------|--------|--------|----|--------|-----|-----|
| Study Day | ≤-14 days ^a | -1 | 1 | 3 | 4 | 5 | 6 | 7 |
| In Hours Post Dose 1 | | -24 | 0 | 48 | 72 | 96 | 120 | 144 |
| Informed consent | X | | | | | | | |
| Demographics | X | | | | | | | |
| Medical History | X | | | | | | | |
| Eligibility Review | X | X | | | | | | |
| Concomitant Medications | X | X | X | X | X | X | | |
| Adverse Events | | X | X | X | X | X | | |
| Physical Exam | C | C | S | S | S | S | | |
| Height & Weight | H/W | W | W | | | | | |
| Vital Signs ^b & Oximetry | X | X | X | X | X | X | | |
| Spirometry ^c | X | X | X | X | X | X | | |
| Chest Xray | X ^d | | | | | | | |
| 12-lead ECG | X | | | | | | | |
| Telemetry | | | X | | | | | |
| CFQ-R RSS ^e | | | X | | | | | |
| Blood for Safety Labs ^f | X | X ^g | X | X | X | | | |
| Urinalysis ^f | U | U ^g | U | U | U | | | |
| Drug Screen ^f | X | | | | | | | |
| Pregnancy Test ^{f,h} | X | X | | | | | | |
| Sputum for Microbiology ^f | | X | | | | | | |
| Blood for CFTR ^f | Genotyping | Sequencing | | | | | | |
| Biomarkers ^f | X | X | | | X | | | |
| Sweat Chloride ^f | X | | | | | | | |
| Randomization | | X | | | | | | |
| Study Drug Administration ⁱ | | | X | X | | X | | |

| Study Procedures | Screening | | Dose 1 | Dose 2 | | Dose 3 | | |
|-------------------------------------|-----------|--|--------|--------|---|--------|--|--|
| Collect Samples for PK ^f | | | X | X | X | X | | |

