APPENDIX 2: SCHEDULE OF LABORATORY TESTS

Table A.2-1: Single Ascending Dose Cohorts 1-4

| Labs | Screening | Check-In | Dose | | | Discharge | | | End of Study ^a | |
|----------------------------------------------------------------|-----------------------------------------------------------------------------------------------------------------------------------------------------------------------------------------------------------------------------------------------------------------------------------------------------------------------------------------------------------------|----------------|----------------|----|----|----------------|----|-----|---------------------------|----------------|
| Study Day | ≤-14 days ^b | -1 | 1 | 2 | 3 | 4 | 5 | 6 | 7 | 8 |
| In Hours | | -24 | 0 | 24 | 48 | 72 | 96 | 120 | 144 | 168 |
| Hematology | X | X | X | X | X | X | | | | X |
| Serum Chemistry | X | X | X | X | X | X | | | | X |
| Hematology & Chemistry | Day 1: Pre-dose, 30, 60 minutes, 2, 4, 8, 12 hours post dose | | | | | | | | | |
| C-Reactive Protein | | X | X | X | | | | | | X |
| Erythrocyte Sedimentation Rate | | X | X | X | | | | | | X |
| C-Reactive Protein & Erythrocyte Sedimentation Rate | Day -1 Day 1: Pre-dose, 24 hours post dose | | | | | | | | | |
| Coagulation and CH50 | X | | | | | | | | | X |
| Direct Antiglobulin Test | X | | | | | | | | | X |
| Serum Tocopherol (Vit. E) | X | | | | | | | | | |
| Urine microalbumin | | X | | | | | | | | X |
| Urinalysis | X | X | X | X | X | X | | | | X |
| | Day 1: On pooled PK samples Day 2, 3, 4, 8: Random sample, preferably 1 st morning void | | | | | | | | | |
| Drug Screen | X ^c | | | | | | | | | |
| Pregnancy test ^d | X | X | | | | | | | | X |
| Sputum for Microbiology | | X | | | | | | | | X |
| CFTR Genotyping ^e | X | | | | | | | | | |
| CFTR Sequencing | | X ^f | | | | | | | | |
| Sweat Chloride | X | | | | | | | | | |
| PK Sampling | Serum: 0, 0.5, 1, 2, 3, 4, 12, 24, 48, 54, 72, 168 hours post dose Urine: Pre-dose; Pooled from 0 to 4, 4 to 12, and 12 to 24 hours post-dose; and 48, 72, and 168 hours post dose (UA on each pooled sample). Sputum: 3 samples obtained within first 6 hours post dose; 24 hours post dose; Day 4 (72 hours post dose); and Day 8 (168 hours post dose) | | | | | | | | | |
| Serum for PK | | | X | X | X | X | | | | X |
| Urine for PK | | | X | X | X | X | | | | X |
| Sputum for PK | | | X ^g | X | | X ^h | | | | X ^g |

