| Direct Antiglobulin Test | X | | | | | | | |
| Serum Tocopherol (Vit. E) | X | | | | | | | |
| Urine microalbumin | | X | | | | | | |
| Urinalysis | X | X | X | X | X | | | |
| | Dose 1: Pre-dose, 0-4, 4-12 hours post dose (UA on each pooled sample) Dose 2: 60 minutes and 4 hours post dose | | | | | | | |
| Drug Screen | X ^b | | | | | | | |
| Pregnancy Test ^c | X | X | | | | | | |
| Sputum for Microbiology | | X | | | | | | |
| CFTR Genotyping ^d | X | | | | | | | |
| CFTR Sequencing | | X ^e | | | | | | |
| Sweat Chloride | X | | | | | | | |
| PK Sampling | Serum: 0, 0.5, 1, 2, 3, 4, 12; pre-Dose 2; 2 hours post Dose 2; 72 hours post Dose 1; 96 hours post Dose 1 (pre-Dose 3) Urine: Pre-dose; Pooled from 0 to 4 and 4 to 12 hours post Dose 1 (UA on each pooled sample). A separate sample should be collected at 72 hours post Dose 1. Sputum: 3 samples obtained within first 6 hours post Dose 1 and Day 4 (72 hours) | | | | | | | |
| Serum for PK | | | X | X | X | X | | |
| Urine for PK | | | X | | X | | | |
| Sputum for PK | | | X ^f | | X | | | |
| Biomarker Sampling | | | | | | | | |
| Blood (serum and plasma) for Biomarkers | X | X ^e | | | X | | | |
| Sputum for Biomarkers | X | X ^e | | | X | | | |

- ^a The screening period for an individual subject may be extended for an additional 7 days at the discretion of the Sponsor's Medical Monitor. See Section 7.2 for details.
- ^b Drug screening may be performed on urine or blood sample.
- ^c Women of child-bearing potential only.
- ^d Required if original documentation for CF genotyping is not available or is earlier than the year 2000.
- ^e Samples may be collected on Day 1 pre-dose instead of Day -1. Samples for CFTR sequencing should not be collected for subjects who participated in SAD cohort.
- ^f Suggest obtaining samples in conjunction with performing spirometry at 10, 60 minutes, and 4 hours post dose.

Table A.2-3: Multiple Ascending Dose Cohorts 5-8, WEEK 2

| Labs | Dose 4 | | Dose 5 | | Dose 6 | | |
|-----------------------------------------------------------------------|------------------------------------------------------------------------|------------|---------------|------------|---------------|------------|------------|
| Study Day | 8 | 9 | 10 | 11 | 12 | 13 | 14 |
| In Hours | 168 | 192 | 216 | 240 | 264 | 288 | 312 |
| Hematology | X | | | | | | |
| Serum Chemistry | X | | | | | | |
| Hematology & Chemistry | Dose 4: Pre-dose, 15, 60 minutes, 2 hours post dose | | | | | | |

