| C-Reactive Protein | X | | | | |
| Erythrocyte Sedimentation Rate | X | | | | |
| C-Reactive Protein & Erythrocyte Sedimentation Rate | Dose 10: Pre-dose | | | | |
| Urine microalbumin | X | | | | |
| Urinalysis | Dose 10: Urine microalbumin pre-dose Dose 10: Urinalysis pre-dose, 60 minutes and 2 hours post dose | | | | |
| Sweat Chloride | | | | | X |
| PK Sampling | Serum: Pre-Dose 10 and 11; Dose 12 (pre-dose; post dose at 1, 2, 3, 4, 8 hours) Urine: Dose 12 pre-dose only | | | | |
| Serum for PK | X | | X | | X |
| Urine for PK | | | | | X |
| Biomarker Sampling | Dose 10: Pre-dose | | | | |
| Blood (serum and plasma) for Biomarkers | X | | | | |
| Sputum for Biomarkers | X | | | | |

Table A.2-6: Multiple Ascending Dose Cohorts 5-8, Follow-up

| Study Procedures | PK Follow-up 24 hours After Last Dose | PK Follow-up 96 Hours After Last Dose | 7 Days After Last Dose (End of Treatment) ^a | 28 Days After Last Dose (End of Study) ^a |
|-----------------------------------------|------------------------------------------------------------------------------------------------------------------------------------------------------------------------------------|---------------------------------------------|-----------------------------------------------------------------|-----------------------------------------------------------|
| Study Day | 27 | 30 | 33 | 54 |
| In Hours Post Dose 1 | 624 ± 12 | 696 ± 96 | 768 | 1272 |
| Hematology | | | X | X |
| Serum Chemistry | | | X | X |
| C-Reactive Protein | | | X | |
| Erythrocyte Sedimentation Rate | | | X | |
| Coagulation and CH50 | | | X | |
| Direct Antibody Test | | | X | |
| Urine microalbumin | | | | X |
| Urinalysis | | | X | X |
| Pregnancy test ^b | | | X | X |
| Sputum for Microbiology | | | X | |
| Sweat Chloride | | | X | X |
| PK Sampling | Serum post last dose: 24 ±12 hrs, 96 ± 48, hours post last dose, and at End of Treatment and End of Study Visit Urine post last dose: 24 ±12 hrs, 96 ± 48, hours post last dose | | | |
| Serum for PK | X | X | X | X |
| Urine for PK | X | X | | |
| Biomarker Sampling | End of Treatment and End of Study Visits | | | |
| Blood (serum and plasma) for Biomarkers | | | X | X |
| Sputum for Biomarkers | | | X | X |

^a See Section 5.5.2 for details on these visits for subjects who withdraw prematurely from the study.

^b Women of child-bearing potential only

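### Item 7 of the Day -1 visit lists (Protocol 7.3.1 and 7.4.2), applied literally, excludes the only scheduled pre-dose urine microalbumin sample, which 8.5 and Appendix 2 require

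*Protocol*

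**What the plan says.** Three parts of the protocol govern laboratory work on Day -1.

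- **Visit lists.** Item 7 of 7.3.1 calls for local blood and urine tests on Day -1 but restricts them to "only assessments that were abnormal but not clinically significant at screening". Item 7 of 7.4.2 sets the same limit for the MAD cohorts.
- **Appendix 1.** Footnote h of Table A.1-1 and footnote g of Table A.1-2, attached to the Day -1 safety blood and urinalysis entries, read: "Only laboratory assessments that are abnormal (but not clinically significant) at screening should be repeated at Day-1".
- **Section 8.5 and Appendix 2.** Section 8.5 states: "Urine microalbumin will be measured at baseline for SAD and MAD cohorts". Tables A.2-1 and A.2-2 leave the microalbumin row blank at screening and mark it on Day -1. For CRP and ESR, 8.5 says: "Two baseline measurements will be made; one on Day -1, and the other prior to dosing on Day 1".

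The later microalbumin samples are Day 8 for SAD (Table A.2-1), before dose 10 for MAD ("Dose 10: Urine microalbumin pre-dose", Table A.2-5) and MAD End of Study (Table A.2-6). Section 7.0 tells sites to consult both appendices for what is due on each study day.

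**The concern.** A test that was not done at screening cannot have been abnormal there. Read as written, item 7 therefore excludes microalbumin on Day -1 for every subject, while 8.5 and Appendix 2 require it for every subject. The two instructions cannot both be followed.

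This is a first-in-human study, and the synopsis names renal toxicity among the laboratory safety targets. Each cohort has six active and two placebo subjects, so reading an unusual microalbumin result depends heavily on that subject's own pre-dose value. Once the first dose is given, a missed pre-dose sample cannot be recovered. Whether a subject has a baseline could come to depend on which part of the protocol the site worked from.

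**Working it through.** The plan gives no figure to reproduce. The check is a cross-reading and a count of scheduled microalbumin samples.

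**Pre-dose samples per subject**

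| Time | Appendix 2 with 8.5 | Visit lists, item 7 taken literally |
|---|---|---|
| Screening | 0 (row blank) | 0 (7.2 item 12 is a general urine item and does not name the test) |
| Day -1 | 1 | 0 (not tested at screening, so not eligible) |
| Day 1 before dosing | 0 (row blank) | 0 (7.3.2 and 7.4.3 ask for urinalysis and PK urine) |
| **Total** | **1** | **0** |

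**Could Day 1 urinalysis supply the value?** Not reliably. The dipstick panel in Protocol 8.5 does not include microalbumin, which has its own sentence there and its own row in Appendix 2. SAP 4.10.2.5 does place microalbumin under urinalysis, but a site collects from the protocol.

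**Does another Day -1 item cover it?** No. Items 8 to 11 separately name the pregnancy test, sputum microbiology, CFTR sequencing and biomarkers. Microbiology and sequencing are, like microalbumin, first done on Day -1, and each has its own item. Microalbumin has none.

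**Post-dose samples per subject (Appendix 2).** SAD: 1 (Day 8). MAD: 2 (before dose 10 on Day 22, and End of Study on Day 54).

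**Across the planned enrolment.** With 32 SAD and 32 MAD subjects:

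- pre-dose values under Appendix 2: 64 × 1 = 64;
- pre-dose values if every site applied item 7 literally: 64 × 0 = 0;
- post-dose values in either case: 32 × 1 + 32 × 2 = 96.

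The 64 and the 0 are bounds. The documents do not show where between them practice would fall.

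**Effect in the SAP.** SAP 4.2.2 sets change from baseline to missing when the baseline is missing. SAP 4.10.2.5 reports urinalysis, with microalbumin included, in listings only. What is lost is the within-subject comparison when the listing is read.

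**Other renal measures.** Creatinine and BUN (serum chemistry) and dipstick protein (urinalysis) are scheduled at screening and on Day 1 before dosing, and item 7 touches neither time. Calculated creatinine clearance follows from creatinine.

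**CRP and ESR.** Neither is scheduled at screening, so item 7 also excludes their Day -1 samples. Planned baselines fall from 2 to 1. The one that remains, Day 1 before dosing, is the most recent pre-dose value and so is the baseline under SAP 4.2.1 and SAP Tables 15 and 16.

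**The case against.** The best case for the plan as it stands has three parts.

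**Section 7.0 sends sites to the appendices, and Appendix 2 marks the sample without a limiting footnote.** A site working from that row would collect it. This stands as a reason to treat the loss as a risk and not a certainty. It does not settle the conflict. Appendix 2 also marks hematology, chemistry and urinalysis on Day -1 without any limit, although item 7 and the Appendix 1 footnotes restrict them. A site cannot tell from Appendix 2 which Day -1 entries are unconditional.

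**The Appendix 1 footnotes speak of tests being repeated.** A first-time test cannot be a repeat, so the footnotes can fairly be read as leaving microalbumin alone. That is correct for the footnotes. Item 7 has no such word, and it is the instruction listed for the visit itself.

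**The visit lists name microalbumin at no visit, so a site that knows to take it after dosing has read Appendix 2 or 8.5 and should know about the baseline.** This has force. But at the post-dose visits the lists ask for local laboratory urine without restriction, so Appendix 2 simply fills in the content. On Day -1 there is an explicit restriction, and a site could use Appendix 2 throughout and still apply that restriction to the whole Day -1 column.

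A reader might go further and infer that the trial loses its renal baseline, that all subjects at some sites will lack one, or that a secondary-endpoint analysis fails. The documents do not support this. Other renal measures keep their baselines, nothing shows how any site would read item 7, and Protocol 13.7.4 plans change-from-baseline summaries for hematology and chemistry, leaving urinalysis to the SAP.

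**Conclusion.** The contradiction is real and narrow. Item 7 of 7.3.1 and 7.4.2, applied as written, reduces scheduled pre-dose microalbumin from one value per subject to none, against the requirement in 8.5 and Appendix 2. For an affected subject, one later value (SAD) or two (MAD) would have no pre-dose comparator.

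This rests on two assumptions: that the site applies item 7 literally, and that it does not add microalbumin to another pre-dose urine sample on its own initiative. No planned summary table is lost, and the baseline used for CRP and ESR does not change. Section 8.5 and Appendix 2 show that the sample was intended, so this is a drafting inconsistency and not a flaw in the design. It is worth correcting because a missed pre-dose sample cannot be taken later.

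**What to change.** Reconcile item 7 of 7.3.1 and 7.4.2 with 8.5 and Appendix 2:

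1. State that the limit applies only to repeats of tests already done at screening.
2. Name urine microalbumin, together with the Day -1 CRP and ESR that 8.5 already requires, as collected on Day -1 in all subjects.
3. Add the same clarification to footnote h of Table A.1-1 and footnote g of Table A.1-2. These already refer to repeats, so they need only the list of tests due in everyone.

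The cost is a change of protocol wording. No sample or visit is added beyond what Appendix 2 schedules, and the SAP analyses need no change.
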